Currently, the first line of treatment for axillary hyperhidrosis is over-the-counter antiperspirants, while effective for normal sweaters, do not provide an adequate solution for most sufferers and are often irritating. Off-label administration of oral anticholinergic medications and topical application with glyopyrronium wipes typically require daily administration and have unappealing systemic side effects. Currently available in-office procedures (including botulinum toxin injections and use of microwave energy), although effective, can be painful and prohibitively expensive. Moreover, a 2016 IHHS survey showed that even though 87.2% of the 1,985 survey participants had received some form of treatment for their excessive sweating, satisfaction with the treatments received a mean score of “below satisfied” (Glaser 2018). Thus, despite some

CANDESANT BIOMEDICAL	CLINICAL STUDY PROTOCOL SAHARA STUDY	Document #: CB-CLP-001 Revision: E
-------------------------	---	---------------------------------------

currently effective treatments to reduce sweating, there remains a need for additional options to help patients reduce axillary sweating for these patients with an approach that is easy to administer with minimal side effects.

To this end, Candesant Biomedical has developed the CDX-101 Patch, which has been renamed the N-SWEAT Patch. This is a non-invasive topical device designed to reduce sweat production in patients who report heavy sweating in the underarms. The patch is applied in a physician's office to the axillae for up to 3-minutes. During treatment, the patch will generate thermal energy in the presence of sweat and is designed to target the sweat glands for inactivation. After this treatment, the patch is completely removed and disposed of by medical staff.

3.3 Early Evidence for N-SWEAT Patch:

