8.7.5 Subject Care and Medications

Subjects will be provided with instructions for post-treatment care. They will be instructed to rinse the area with water or cleanse with soap and water if they feel any discomfort. Deodorant will be provided for use during study participation.

CANDESANT BIOMEDICAL	CLINICAL STUDY PROTOCOL SAHARA STUDY	Document #: CB-CLP-001 Revision: E
-------------------------	---	---------------------------------------

Subjects may take over-the-counter pain medication as needed following treatment. Acetaminophen is recommended for pain control. Prescription strength pain medication is not expected to be necessary.

Subjects must refrain from using over-the-counter or prescription, prescription-strength, or clinical strength topical aluminum compounds or antiperspirants for the duration of study participation. An approved deodorant (without antiperspirant) will be provided at screening for convenience. Other deodorants without antiperspirant may be allowed; however, they must be approved by the investigator. Subjects must also refrain from using topical steroids or hair removal creams on the treatment areas.

Subjects must refrain from taking anticholinergic medications, beta blockers, calcium channel blockers, other systemic treatments, or medications that are known to cause heavy sweating during the study. If one or more of these medications or treatments are required, and in the opinion of the investigator would compromise study results, the subject will be followed for safety only. All relevant medications taken will be documented.

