8.10 Study Exit or Premature Withdrawal

Subjects will be formally exited from the study through the completion of the Study Exit CRF at the time of study completion, provided the subject has not experienced an AE directly attributable to the study device or procedure that is ongoing and unstable and/or unexplained.

Subjects may be prematurely terminated or withdrawn from the study for the following reasons:

- Not eligible for treatment
- Subject starts a medication or treatment that, in the opinion of the investigator, may skew study results
- Lost to follow-up (following 3 documented attempts to reach subject)
- In the investigator's opinion, it is not in the best interest of the subject to continue study participation
- Voluntary withdrawal, meaning that the subject voluntarily chooses not to participate in the study

All subjects enrolled (including those prematurely withdrawn) shall be accounted for and documented.

CANDESANT BIOMEDICAL	CLINICAL STUDY PROTOCOL SAHARA STUDY	Document #: CB-CLP-001 Revision: E
-------------------------	---	---------------------------------------

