6.4 Full Analysis Set

The full-analysis set (FAS) is those ITT subjects that have evaluable data for the endpoint.

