9. HANDLING OF MISSING DATA FOR THE PRIMARY EFFICACY ENDPOINT

A sensitivity analysis to the missing data in the ITT sample will be conducted for the primary efficacy endpoint. The sensitivity analysis will include a best case, worst case and tipping point analysis. The best case analysis will impute successes for subjects randomized to treatment with missing data and failures for subjects randomized to sham with missing data. The worst case analysis will impute failures for subjects randomized to treatment with missing data and success for subjects randomized to sham with missing data. The tipping point analysis completes the matrix of imputations possible between the best case and worst analysis to determine where statistical significance is maintained or lost. If the worst case analysis maintains statistical significance, the tipping point analysis is not necessary.

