11. EFFICACY ANALYSIS

11.1 Primary Efficacy

The proportion of subjects with HDSS of 1 or 2 at 4-weeks in subjects randomized to treatment (p_T) will be higher than that in subjects randomized to sham (p_S).

Subjects Included in Analysis: All ITT subjects.

Endpoint(s): The proportion of subjects with HDSS of 1 or 2 at 4 weeks of follow-up.

Hypothesis:

H_0 : The proportion of subjects with HDSS of 1 or 2 at 4-weeks in subjects randomized to treatment (p_T) will be lower than or equal to that in subjects randomized to sham (p_S), $p_T \leq p_S$

H_a : The proportion of subjects with HDSS of 1 or 2 at 4-weeks in subjects randomized to treatment (p_T) will be greater than that in subjects randomized to sham (p_S), $p_T > p_S$

Sample Size Rationale: . The sample size and power calculations for the randomized cohort are based on the company's clinical trial data as well as on published data (Glaser et al., 2012). To account for substantial variability in the proportion of responders across various trials, multiple scenarios were considered.

Per definition of the primary endpoint a responder is a patient with HDSS values of 1 or 2 at 4-weeks post treatment. If proportions of responders in the treated vs. sham arms are 85% vs. 60%, respectively, then using PASS 2019, testing two proportions using the Mantel-Haenszel test, 50 patients per arm will be needed to detect the treatment difference with the 80% power at the 0.05 two-sided significance level. If proportions of responders in the

treated vs. sham arms are 73% vs. 44%, then 45 patients per arm will be needed. The evaluable sample size of 50 patients per arm was chosen

Primary Statistical Analysis: The proportion of patients with HDSS of 1 or 2 at 4 weeks post-treatment will be compared between treatment vs. sham using the Cochran-Mantel-Haenszel (CMH) test stratified by baseline HDSS value of 3 vs. 4 in the FAS population. Statistical significance is achieved with two-sided p-value <0.05 equivalent to one-sided p-value < 0.025.

Additional Statistical Analysis: Additional analyses include those summarized in **Section 8.3** Evaluation for Pooling of Data and **Section 9** Handling of Missing Data for the Primary Efficacy Endpoint. The primary statistical analysis will be completed in the PP population as well.

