Statistical Analysis: A Kaplan-Meier product limit method will be used for the analysis. Time 0 will be the treatment date. For subjects who do not respond to treatment, the duration of treatment will be 0. For subjects who do respond to treatment, the event is the first subsequent week of follow-up after the 4 week follow-up in which the subject reported an HDSS of 3 or 4 or censoring from the study either due to drop-out or completing the study without reverting to HDSS 3 or 4. The study groups will be compared using the Log-Rank statistic stratified by HDSS 3 or 4 at baseline.

This analysis will be completed for reversion to the patient's baseline value and in the PP group as well.

11.3.5 To compare mean change from baseline at 4 weeks in GSP between subjects randomized to treatment as compared to sham.

Subjects Included in Analysis: All FAS subjects will be included in the analysis.

Endpoint(s): The average of 2 accurate GSP measurements will be conducted for each Axilla at each time point. The total sweat production at each timepoint will be calculated by summing the average sweat production from both axilla. The change in GSP at 4 weeks will be calculated by subtracting the total sweat production at baseline from the total value at 4 weeks.

Statistical Analysis: An analysis of variance model will be used to compare average change in total GSP at 4 weeks as compared to baseline between randomized groups. The dependent variable is change in total GSP at 4 weeks as compared to baseline with independent variables to include randomized group, baseline HDSS, and two-way interaction terms.

A hierarchical stepwise backward elimination technique will be used to reduce the model. The two-way interactions will be reviewed first, the two-way interaction with the largest p-value provided that p-value is greater than 0.05 will be removed from the model and the model refit and repeated until only two-way interactions with p-values < 0.05 are retained. The main effects for any two-way interaction retained in the model must remain in the model as well as the randomized treatment. That being said, the main effects will be evaluated in the same manner as the two-way interaction terms. This analysis will be repeated in the PP population.

11.3.6 To compare responses to additional QOL questions from baseline throughout follow-up, as appropriate between subjects randomized to treatment as compared to sham.

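### A subject who starts a restricted medicine can move to safety-only follow-up on the investigator's opinion, lose the week-4 HDSS and so leave the primary test

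*Protocol*

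**What the plan says.** Protocol 8.7.5 sets the restriction: "Subjects must refrain from taking anticholinergic medications, beta blockers, calcium channel blockers, other systemic treatments, or medications that are known to cause heavy sweating". If such a medicine or treatment becomes necessary and "in the opinion of the investigator would compromise study results, the subject will be followed for safety only". Relevant medicines are to be documented. Section 8.10 lists among the grounds for premature termination or withdrawal: "Subject starts a medication or treatment that, in the opinion of the investigator, may skew study results". Safety-only follow-up is not defined. No section says that the HDSS or QoL surveys go on after this point.

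Protocol 3.2 describes some of the restricted medicines as existing treatments for the condition: "Off-label administration of oral anticholinergic medications and topical application with glyopyrronium wipes typically require daily administration".

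The SAP states that it supersedes the protocol's analyses. Its section 6.4 reads: "The full-analysis set (FAS) is those ITT subjects that have evaluable data for the endpoint". Section 11.1 names all ITT subjects as included, but the deciding comparison is the "Cochran-Mantel-Haenszel (CMH) test stratified by baseline HDSS value of 3 vs. 4 in the FAS population". For missing week-4 HDSS, section 9 adds: "The sensitivity analysis will include a best case, worst case and tipping point analysis". It applies to the primary endpoint only.

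For duration of efficacy (SAP 11.3.4), the event in a responder is the first weekly HDSS of 3 or 4 after week 4. Otherwise the subject ends with "censoring from the study either due to drop-out or completing the study without reverting to HDSS 3 or 4". Neither document treats the start of a restricted medicine as non-response or as reversion.

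**The concern.** Starting a medicine that reduces sweating happens after randomisation and may be a consequence of the outcome: a subject whose sweating persists or returns has a reason to want one. On the plain reading of 8.7.5, the plan then stops collecting the outcome, at the discretion of one person. The week-4 HDSS that goes missing could have been collected, because the weekly surveys are electronic and the 4-week visit is already required.

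Two things are at stake. At week 4, non-responders who leave the FAS raise the observed response rate in their arm, and the contrast moves if the two arms lose different numbers. After week 4, a responder removed before reporting HDSS 3 or 4 is censored when the effect may be ending. Protocol 8.9 calls duration of effect an important outcome.

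**Working it through.** **Inputs.** Response rates of 85% vs 60% and 73% vs 44%, two-sided 0.05, 80% power, and 50 and 45 evaluable per arm (Protocol 9.10.1, SAP 11.1). 55 randomised per arm after 10% attrition (Protocol 9.3, SAP 4). Expected effect of 6 to 8 weeks on average (Protocol 4.3). **Assumed, because the documents give no figure:** q, the share of week-4 non-responders moved to safety-only follow-up before week 4, at 10 to 30%.

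**The plan's own figure.** The pooled-variance formula without continuity correction gives 49 per arm for 85/60 (stated 50) and 45 for 73/44 (stated 45). The sample size reproduces and is not in dispute.

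**Effect on the FAS.** If a share q of non-responders is lost, the observed rate is p / [p + (1 − p)(1 − q)]. For q = 10%: 0.85 / (0.85 + 0.15 × 0.90) = 86.3%, and 0.60 / (0.60 + 0.40 × 0.90) = 62.5%. Power below is for the subjects left out of 55 per arm, assuming no other attrition.

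| q, both arms | 85/60: observed rates | Difference (points) | Power, normal approximation | Power, simulated CMH | 73/44: difference (points) | Power, normal approximation |
|---|---|---|---|---|---|---|
| 0 | 85.0 / 60.0 | 25.0 | 84.5% | 85.1% | 29.0 | 88.1% |
| 10% | 86.3 / 62.5 | 23.8 | 81.5% | 82.2% | 28.4 | 85.9% |
| 20% | 87.6 / 65.2 | 22.4 | 77.7% | 78.8% | 27.6 | 83.1% |
| 30% | 89.0 / 68.2 | 20.8 | 73.2% | 74.3% | 26.5 | 79.6% |

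The simulated column uses 400,000 trials and the unstratified form of the test.

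**Unequal loss, 85/60.** If only sham failures are lost at q = 20 to 30%, the difference falls to 19.8 to 16.8 points and power to about 66 to 53%. If only treated failures are lost, the difference is inflated to 27.6 to 29.0 points.

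**Unequal loss, no true effect.** With both arms at 60% and only treated failures lost at q = 20%, the treated rate reads 0.60 / (0.60 + 0.40 × 0.80) = 65.2%, a spurious 5.2 points. The chance of a significant result favouring treatment is then 7.9%, against a nominal 2.5%. At q = 30% it is 13.5%. With both arms at 44% the figures are 8.1% and 14.1%.

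**Duration.** Responders were simulated with exponential reversion from week 4, weekly reports and follow-up to week 12. A share of reverters was censored one week before the report that would have shown HDSS 3 or 4. A true week-7 Kaplan-Meier median reads week 8 when 10 or 20% of reverters are censored this way, and week 9 at 30 or 40%. The estimated share still responding at week 12 rises from 16% to between 19% (10% censored) and 32% (40% censored).

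**The case against.** Much can be said for the plan.

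- **The trigger is narrow and often unrelated to outcome.** The medicine must be required, and the investigator must judge that it compromises results. Beta blockers and calcium channel blockers would mostly be needed for other conditions, and medicines that cause sweating are the opposite of rescue. Whether the rule reaches antiperspirants, which are in the preceding paragraph of 8.7.5, is unclear. This stands: the loss may depend on outcome, but the documents do not show that it will.
- **The assumed shares have no source.** At 60% sham response, q = 30% means 0.40 × 0.30 = 12% of the sham arm within four weeks, among subjects who agreed at entry (criterion I-6) to avoid anticholinergics. At q = 10% the expected loss is 55 × 0.15 × 0.10 = 0.8 treated and 55 × 0.40 × 0.10 = 2.2 sham subjects, within the allowance of 5 per arm, and power stays above 80%. This stands.
- **Section 9 helps.** If only treated failures are lost, its worst case counts them as failures and exposes the inflated contrast. This stands in part. These are sensitivity analyses beside a deciding test that still omits the subjects. They treat the subjects as ordinary missing data, and they do not cover the secondary or duration endpoints.
- **Weekly surveys would usually catch a reversion first.** HDSS 3 or 4 would normally be reported before a medicine is obtained, and that report is the event. This stands. A reversion is lost only when the medicine comes first, and the endpoint is observational and not meant to support claims (SAP 11.3).

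A reader might also infer that the rule must remove more sham failures and so shrink the contrast. Nothing in the documents fixes that direction.

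**Conclusion.** The point holds as an avoidable source of missing primary data, decided by opinion and possibly related to outcome. It does not show that the trial is biased in a known direction. It rests on the plain reading that safety-only follow-up ends HDSS collection, which 8.10 reinforces but neither document states.

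The size depends wholly on the assumed q. With equal loss of 10, 20 or 30% of non-responders from 55 per arm at 85/60, power goes from about 85% to 82, 79 or 74%. With loss of 20 to 30% of treated failures only, one-sided error is about 8 to 14%.

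Two stronger readings are not supported. One would take the loss from 50 per arm; but 50 is the evaluable number after attrition, and starting there assumes that the allowance is already spent. The other would multiply the median duration by 1/(1 − q), so that 7 weeks reads 7 / 0.7 = 10.0 at 30%. The SAP counts events only after week 4 and on weekly reports, and under that definition a true week-7 median reads about week 8 to 9. Even that applies only to reversions that no survey recorded first.

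**What to change.** **Protocol 8.7.5, and 8.10 for this reason only.** State that starting a restricted medicine does not by itself end efficacy data collection. The scheduled weekly HDSS and QoL surveys and the 4-week visit continue unless the subject withdraws or is withdrawn for another listed reason, including the investigator's best-interest ground. Record the medicine and its start date. Sections 8.7.5 and 8.10 must be reconciled on what follows from the trigger. Who may take which medicine is unchanged.

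**SAP 11.1.** Keep these subjects in the primary analysis with their observed week-4 HDSS. Add a sensitivity analysis in which starting any treatment on a prespecified list of sweat-reducing treatments before week 4 counts as non-response.

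**SAP 11.3.4.** Add a sensitivity analysis in which starting a listed treatment after week 4 counts as a reversion on that date.

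**Cost.** A protocol amendment with its FDA and IRB submissions, a short list to agree before unblinding, and a little extra analysis. No visits or surveys are added to the schedule. The downside is that some observed HDSS values will reflect the other medicine rather than the patch; the sensitivity analyses show how much that matters.

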8.8 Follow-up Evaluations

Subjects will undergo phone evaluations at 24 hours (\pm 12 hours) and 2-weeks (\pm 2 days) following treatment, at which time subjects will be asked about their discomfort and if they may have experienced an AE. If the subject has symptoms, a telehealth or clinical visit should be scheduled to assess the subject's condition within 24 hours. Any concern for burn injury should result in an in-person clinic visit. Please refer to Appendix G for conditions under which subjects should be referred to the burn center.

A follow-up visit is required at 48-72 hours post-treatment. Visit will include a physical exam, assessment of vitals, and treatment site assessment. Any new treatment area symptoms should result in a telehealth or clinic visit being scheduled (within 24 hours) to assess the subject's conditions. Any concern for burn injury should result in an in-person clinic visit. In addition, a written daily dairy will be provided to subjects to record treatment site pain or other symptoms.

Beginning 1-week post treatment, the subject will be asked to complete the HDSS and QoL surveys electronically once per week. The survey may be taken electronically via cell phone, tablet or computer. The subject will receive instructions at the baseline visit. Subject will be reminded to complete the surveys via text or email, per their preference. In the event that the electronic submission is not possible, the subject will be asked to complete the surveys on paper and mail it to the clinic. If a subject fails to complete the survey in a timely matter the site will be notified so that they can make contact with the study subject.

Subjects will be asked to schedule follow-up evaluations at 2-week intervals starting on 4-weeks (i.e. 4-, 6-, 8-, 10-, and 12-weeks post-treatment). However, **the 4-week visit is required to take place as an office visit**. The rest of the visits are recommended to take place in person but may be conducted by phone if an office visit is not possible or

CANDESANT BIOMEDICAL	CLINICAL STUDY PROTOCOL SAHARA STUDY	Document #: CB-CLP-001 Revision: E
-------------------------	---	---------------------------------------

practical. If at any time, the subject reports local skin reaction or an adverse event, a clinic visit should be scheduled for direct assessment by the study medical team.

When possible, subjects are to undergo follow-up visit evaluations at the same time of day of the week and around the same time of day as their baseline evaluations. In the event that the subject is not able to report on the same day as the baseline evaluations, the visit window permits the subject to report up to 1-3 days earlier or later than the target weekday. The visit windows are shown in **Table 3** below.

Table 3. Visit Windows

Visit	Window
24-hour phone call	± 12 hours
48-72 hour visit	± 1 day
2-week phone call	± 2 days
4-week, 6-week, 8-week, 10-week, 12-week visits	± 3 days

Follow-up evaluations to be conducted at follow-up visits are summarized below in **Table 4**.

Table 4. Follow-Up Assessments

Assessment	Time	Method	Reference
Daily Diary	Daily through 4-weeks	Written journal returned at 4-week visit	Appendix F
HDSS	Weekly	Visit or electronic	Appendix A
QoL Assessments	Weekly	Visit or electronic	Appendix C
Assessment for Local Skin Reactions	Immediately post treatment, AND, at every clinic visit	Visit required	Appendix B
GSP*	4-weeks ONLY	Visit required	Appendix D

**NOTE: If excess hair is present on the axilla at the 4-week visit, the hair shall be clipped prior to conducting GSP testing. Stubble or minimal hair is acceptable. GSP should be measured in accordance with the instructions and training provided by the sponsor. Any deviation from this procedure should be documented and explained.*

Table 5 summarizes the subject schedule for the study.

8.9 Extended Follow-Up Cohort

An important outcome to be assessed by the Sahara Study is the duration of the effect of the N-SWEAT Patch Treatment. Therefore, subjects that reach the final Sahara Study visit (12 weeks) and are still responding to treatment (i.e. HDSS has not returned to Baseline) will be invited to continue follow-up by enrollment into an Extended Follow-Up Cohort. Eligible subjects will provide consent prior to being enrolled into this cohort, within 4 weeks of completing their 12-week visit.

Subjects enrolled in this cohort will not undergo any additional treatment, their participation will include extended follow-up only through 24-weeks post treatment or when HDSS returns to Baseline (whichever occurs first)

Subjects enrolled into the Extended Follow-Up Cohort will be asked to continue weekly electronic surveys until participation is complete. Phone Calls shall be scheduled with subjects in this cohort by the site study team at 16-weeks, 20-weeks and 24-weeks post treatment during participation.

Table 5. Subject Visit Schedule

														Week 12			
			24 hours	48-72 hours	Week 1	Week 2	Week 3	Week 4	Week 5	Week 6	Week 7	Week 8	Week 9	Week 10			
			±12 hrs	±1 day	± 2 days	All other follow-up visits window include ± 3 days											
Clinical Visit Required	X	X		X			X										
Clinical Evaluation (Visit Recommended)									X		X		X		X		X
Clinical Evaluation (Phone Call Required, Visit if symptomatic)				X		X											
Daily Diary					Daily completion through 4-week visit												
ELECTRONIC ASSESSMENTS (cell phone, tablet, computer)																	
HDSS					X	X	X	X	X	X	X	X	X	X	X	X	
QoL-7			X		X	X	X	X	X	X	X	X	X	X	X	X	
QoL (Bother and Impact)			X		X	X	X	X	X	X	X	X	X	X	X	X	
Additional QoL Assessments			X		X	X	X	X	X	X	X	X	X	X	X	X	
HDSS by Site	X	X															
GSP	X	X						X									
Assessment for Local Skin Reactions	X	X							X ¹		X ¹		X ¹		X ¹		
Physical Exam	X	X							X ¹		X ¹		X ¹		X ¹		
Pregnancy Test (for women of child-bearing potential ONLY)	X																
Assessment for AEs since last visit			X					X		X		X		X		X	

¹ To be conducted at all clinic visits

CANDESANT BIOMEDICAL	CLINICAL STUDY PROTOCOL SAHARA STUDY	Document #: CB-CLP-001 Revision: E
---------------------------------	---	---------------------------------------

